13.4.1.1. Study Phases for Concomitant Medication

Study Phase	Definition
Prior	If medication end date is not missing and is before 28 days, prior to screening visit
Concomitant	Any medication that is not a prior

NOTES:

- Please refer to [Appendix 7: Reporting Standards for Missing Data](#) for handling of missing and partial dates for concomitant medication. Use the rules in this table if concomitant medication date is completely missing.

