1.3. Schedule of Activities (SoA)

Part A- Single Dose										
Procedure	Screening (up to 30 days before Day 1)	Treatment Period [Days] (for each dosing period)						E.D.	Follow-up (~14±1 days post last dose)	Notes E.D = early discontinuation/withdrawal
		-2	-1	1	2	3	4			
Informed consent	X									
Inclusion and exclusion criteria (including drug screens)	X			X						Recheck clinical status before randomization and/or 1st dose of study medication.
Demography	X									
Physical examination including height and weight	F	B					B	(B)	F	F: Full exam; B: Brief Exam; height is only taken once at screening
Medical history (includes substance usage and family history of premature cardiovascular (CV) disease and any changes in health status occurring between screening and admission to the unit)	X	X								Substances: Drugs, Alcohol, tobacco, and caffeine
Past and current medical conditions	X	X								

Part A- Single Dose										
Procedure	Screening (up to 30 days before Day 1)	Treatment Period [Days] (for each dosing period)						E.D.	Follow-up (~14±1 days post last dose)	Notes E.D = early discontinuation/withdrawal
		-2	-1	1	2	3	4			
Human Immunodeficiency Virus (HIV), Hepatitis B and C screening	X									If test otherwise performed within 3 months prior to first dose of study intervention, testing at screening is not required
Admission to Clinical Unit		X								
Safety Laboratory assessments (include liver chemistries)	X	X		X	X	X	X	(X)	X	Predose; 8 hr, 24 hr, and, 48 hr, and 72 hr post-dose and at follow-up visit
Routine Urinalysis	X			X	X	X	X	(X)	X	Predose; 8 hr, 24 hr, 48 hr, and 72 hr post-dose and at follow-up visit
12-lead Electrocardiogram (ECG)	X	X		←-----X-----→				(X)	X	ECGs assessed at screening (triplicate) and admission (single). During treatment period ECGs assessed predose (triplicate at least 5 minutes (min) intervals) and single measurements postdose every 30 min for 1 hr, hourly up to 6 hr, and at 12 hr, 24 hr, 36 hr and 48 hr and 72 hr post-dose

Part A- Single Dose										
Procedure	Screening (up to 30 days before Day 1)	Treatment Period [Days] (for each dosing period)						E.D.	Follow-up (~14±1 days post last dose)	Notes E.D = early discontinuation/withdrawal
		-2	-1	1	2	3	4			

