5.2. Exclusion Criteria

Participants are excluded from the study if any of the following criteria apply:

Medical Conditions

1. History or presence of cardiovascular, respiratory, hepatic, renal, gastrointestinal, endocrine, hematological, or neurological disorders capable of significantly altering the absorption, metabolism, or elimination of drugs; constituting a risk when taking the study intervention; or interfering with the interpretation of data.
2. Any clinically significant abnormal vital signs
3. Lymphoma, leukemia, or any malignancy within the past 5 years except for basal cell or squamous epithelial carcinomas of the skin that have been resected with no evidence of metastatic disease for 3 years
4. Alanine transaminase (ALT) >1.5x upper limit of normal (ULN)
5. Bilirubin >1.5xULN (isolated bilirubin >1.5xULN is acceptable if bilirubin is fractionated and direct bilirubin <35%).
6. Current or chronic history of liver disease, or known hepatic or biliary abnormalities (with the exception of Gilbert's syndrome or asymptomatic gallstones)
7. QTc >450 msec

NOTES:

- The QTc is the QT interval corrected for heart rate according to Fridericia's formula (QTcF), machine-read or manually over-read.
- The specific formula that will be used to determine eligibility and discontinuation for an individual subject should be determined prior to initiation of the study. In other words, several different formulae cannot be used to calculate the QTc for an individual subject and then the lowest QTc value used to include or discontinue the subject from the trial.

Prior/Concomitant Therapy

8. Unable to refrain from the use of aspirin, NSAIDs, vitamins, herbal and dietary supplements (including St John's Wort) within 10 days prior to the first dose of study medication (Specific medications listed in [Section 6.5](#) may be allowed).

Prior/Concurrent Clinical Study Experience

9. Where participation in the study would result in loss of blood or blood products in excess of 500 mL within 56 days
10. Exposure to more than 4 new chemical entities within 12 months prior to the first dosing day.
11. Current enrolment or past participation within the last 30 days before signing of consent in this or any other clinical study involving an investigational study intervention or any other type of medical research.

Diagnostic assessments

12. Presence of Hepatitis B surface antigen (HBsAg) at screening
13. Positive Hepatitis C antibody test result at screening.

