6.5. Concomitant Therapy

Any medication or vaccine (including over-the-counter or prescription medicines, vitamins, and/or herbal supplements) that the participant is receiving at the time of enrollment or receives during the study must be recorded along with:

- reason for use
- dates of administration including start and end dates
- dosage information including dose and frequency

The Medical Monitor should be contacted if there are any questions regarding concomitant or prior therapy.

Participants must abstain from taking prescription or nonprescription drugs, including vitamins and dietary or herbal supplements (including St. John's Wort) within 10 days (or 14 days if the drug is a potential enzyme inducer) or 5 half-lives (whichever is longer) before the start of study intervention until completion of the follow-up visit, unless, in the opinion of the investigator and sponsor, the medication will not interfere with the study.

Due to potential effects on GSK3439171A's related pathways, neither aspirin nor NSAIDS of any kind are permitted for use from 10 days prior to the start of the study through the follow-up visit. Acetaminophen or another medication selected by the investigator and the Medical monitor may be administered as prescribed (acetaminophen not to exceed 4,000 mg/24 hr per current guidelines) by attending study staff if simple analgesia is required during the study. Local anaesthesia will be used for muscle biopsy procedures. Other concomitant medication may be considered on a case-by-case basis by the investigator in consultation with the Medical Monitor.

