13.4. Appendix 4: Study Phases and Treatment Emergent Adverse Events

13.4.1. Study Phases

Assessments and events will be classified according to the time of occurrence relative to study treatment

Study Phase	Definition
Pre-Treatment	Date ≤ Study Treatment Start Date
On-Treatment	Study Treatment Start Date < Date ≤ Study Treatment Stop Date + 3 days
Post-Treatment	Date > Study Treatment Stop Date + 3 days

Note: Estimated half-life of GSK3439171 is approx. 13 hours. The maximum of (5 half-lives ~ 65 hours ~ 3days) and after the Study Treatment End Date, lag time have been considered to be 3 days to define the end of treatment phase.

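### The prior-medication cut-off is set from screening rather than first dose, so recorded drugs washed out before dosing are counted as concomitant in Tables 1.30 to 1.32

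*SAP*

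**What the plan says.** SAP 13.4.1.1 has two classes. A medication is Prior on one condition: "If medication end date is not missing and is before 28 days, prior to screening visit". Concomitant is the remainder: "Any medication that is not a prior". The general phase table just above it, in SAP 13.4.1, uses a different anchor and defines pre-treatment as "Date ≤ Study Treatment Start Date". SAP 13.7.2.1 deals only with missing and partial medication dates and leaves the class boundary where it is.

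The protocol sets the washouts from the start of dosing. Protocol 6.5 bars prescription and non-prescription drugs for a stated period ahead of dosing, worded as "within 10 days (or 14 days if the drug is a potential enzyme inducer) or 5 half-lives (whichever is longer) before the start", with an exception where the investigator and sponsor judge that a drug will not interfere. Exclusion criterion 8 (Protocol 5.2) removes anyone unable to stay off aspirin, NSAIDs, vitamins and supplements "within 10 days prior to the first dose of study medication". The schedule in Protocol 1.3 allows "Screening (up to 30 days before Day 1"). On data capture, Protocol 6.5 covers any medication the participant is "receiving at the time of enrollment or receives during the study must be recorded", with start and end dates.

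The displays affected are Tables 1.30 to 1.32, which summarise concomitant medications for Parts A, B and C by cohort. No summary table of prior medications is listed.

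**The concern.** A reader takes a concomitant-medication table to show drugs used while study treatment was being given. Under this rule it also shows drugs that were stopped before the first dose, including those stopped because the protocol required it. A participant who followed the washout looks the same in the table as one who took a prohibited drug on treatment. NSAIDs make this awkward, because Protocol 6.5 bars them for their possible effect on the drug's own pathway.

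The SAP is also inconsistent with itself. SAP 13.4.1 classifies by treatment start, whereas its medication subsection uses a date before screening and gives no reason. SAP 6.1 promises analyses of both prior and concomitant medications, but the rule leaves little or nothing in the Prior class.

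**Working it through.** The plan states no figure to reproduce. The check is date arithmetic on the rule.

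**Inputs.** Let *s* be the number of days from screening to first dose, with *s* ≤ 30 (Protocol 1.3). Let *e* be the number of days before first dose on which a drug was stopped. The look-back is 28 days (SAP 13.4.1.1). The fixed washouts are 10 and 14 days (Protocol 6.5; exclusion 8 for NSAIDs and supplements).

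**Step 1: the rule as written.** A drug is Prior only if *e* > *s* + 28. Otherwise it is Concomitant.

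| Screening, *s* | Cut-off, *s* + 28 | Stopped at 10 | Stopped at 14 | Stopped at 31 | Stopped at 59 |
|---|---|---|---|---|---|
| 2 | 30 | Concomitant | Concomitant | Prior | Prior |
| 10 | 38 | Concomitant | Concomitant | Concomitant | Prior |
| 14 | 42 | Concomitant | Concomitant | Concomitant | Prior |
| 30 | 58 | Concomitant | Concomitant | Concomitant | Prior |

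The cut-off can never be less than 28 days before first dose, and 10 and 14 are both below 28. No permitted screening date makes a 10- or 14-day washout Prior. A washout based on 5 half-lives is Prior only if it ended more than *s* + 28 days before dosing.

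**Step 2: which drugs reach the tables.** Protocol 9.3 defines enrolled participants as those who sign the consent form, and consent is a screening procedure in Protocol 1.3. Taking the two as the same day, a drug must be recorded only if *e* ≤ *s* or it was taken later. Prior status needs *e* > *s* + 28. No required record satisfies both, so the Prior class holds only drugs recorded beyond the requirement.

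The misclassified required records are those with 1 ≤ *e* ≤ *s*, a window of at most 30 days. A compliant 10-day washout is a required record when *s* is 10 to 30, and a compliant 14-day washout when *s* is 14 to 30.

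**Step 3: an example.** A participant is screened 25 days before first dose while taking an NSAID, and stops it 15 days before first dose.
- Exclusion 8 is met, because 15 ≥ 10.
- The drug must be recorded, because 15 ≤ 25.
- The cut-off is 25 + 28 = 53 days. As 15 < 53, the drug is Concomitant.
- Under a first-dose rule it is Prior.

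**Step 4: after re-anchoring.** The span of pre-dose stop days labelled Concomitant is now 30 to 58 for the screening dates in the table. It falls to 0 if Prior means ended before first dose.

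**The case against.** The case for leaving the rule alone is reasonable. A look-back in a descriptive medication table is partly a reporting choice, and this one errs towards inclusion, since no drug taken on treatment is dropped. Participants are healthy and few entries are likely. Start and end dates are collected, and Listings 29 to 31 are planned, so a reader may be able to check individual records. Prohibited use on treatment belongs in the protocol-deviation displays.

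All of that bears on importance and stands. It does not make the summary count correct: the tables would still label compliant pre-dose washouts as concomitant use.

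A reader might infer more than the documents support:
- **That drugs stopped up to 58 days before dosing will appear.** 30 + 28 = 58 is the theoretical reach. With screening at 30 days, a drug stopped 31 to 58 days before dosing had ended before enrollment and need not be recorded.
- **That every drug stopped before first dose is misclassed.** One that ended more than 28 days before screening is correctly Prior.
- **That the interpretation of adverse events, liver tests or prostaglandin markers is affected.** No analysis in SAP sections 7, 8 or 10 uses the Prior/Concomitant class. The tables are by cohort and could not link a drug to a particular period's result under either definition.

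**Conclusion.** The point holds as a labelling error of small consequence. The SAP's rule counts any recorded drug stopped between 28 days before screening and first dose as concomitant, and that always includes the fixed 10- and 14-day washouts. In practice the window is screening to first dose, up to about 30 days, and the Prior class is close to empty.

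This rests on two assumptions: sites record what Protocol 6.5 requires and little more, and enrollment falls on the screening date. For NSAIDs it uses the first-dose wording of exclusion 8. The documents give no basis for estimating how many entries would be affected. No estimate, confidence interval or planned safety comparison changes.

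**What to change.** In SAP 13.4.1.1, define Prior as a medication with a non-missing end date before the first dose of study treatment. Define Concomitant as any medication taken on or after the first dose, or with a missing end date. Partial dates can stay under SAP 13.7.2.1. No display by period is needed, because Tables 1.30 to 1.32 are by cohort.

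State also that Listings 29 to 31, whose titles refer only to concomitant medications, will show all recorded drugs with a class flag, so that Prior drugs do not vanish from the report.

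The cost is a short text change and one derivation, using dates that Protocol 6.5 already requires.

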13.5. Appendix 5: Data Display Standards & Handling Conventions

13.5.1. Reporting Process

Software	

 The currently supported versions of SAS software will be used. 	
Reporting Area	
HARP Server	: us1salx00259
HARP Compound	: /arenv/arprod/gsk3439171/mid209275/final_01
Analysis Datasets	

 Analysis datasets will be created according to CDISC standards (SDTM IG Version 3.2 & ADaM IG Version 1.0) 	
Generation of RTF Files	

 RTF files will be generated for SAC. 	

13.5.2. Reporting Standards

General	

 The current GSK Integrated Data Standards Library (IDSL) will be applied for reporting, unless otherwise stated (IDSL Standards Location: https://spope.gsk.com/sites/IDSLLibrary/SitePages/Home.aspx): 
 4.03 to 4.23: General Principles 5.01 to 5.08: Principles Related to Data Listings 6.01 to 6.11: Principles Related to Summary Tables 7.01 to 7.13: Principles Related to Graphics Do not include subject level listings in the main body of the GSK Clinical Study Report. All subject level listings should be located in the modular appendices as ICH or non-ICH listings 	
Formats	

 GSK IDSL Statistical Principles (5.03 & 6.06.3) for decimal places (DP's) will be adopted for reporting of data based on the raw data collected, unless otherwise stated. Numeric data will be reported at the precision collected on the eCRF. 	

 The reported precision from non eCRF sources will follow the IDSL statistical principles but may be adjusted to a clinically interpretable number of DP's. 	
Planned and Actual Time	

 Reporting for tables, figures and formal statistical analyses: 
 Planned time relative to dosing will be used in figures, summaries, statistical analyses and calculation of any derived parameters, unless otherwise stated. The impact of any major deviation from the planned assessment times and/or scheduled visit days on the analyses and interpretation of the results will be assessed as appropriate. Reporting for Data Listings: 
 Planned and actual time relative to study drug dosing will be shown in listings (Refer to IDSL Statistical Principle 5.05.1). Unscheduled or unplanned readings will be presented within the subject's listings. 	
Unscheduled Visits	

 Unscheduled visits will not be included in summary tables and/or figures. However, for baseline consideration if the latest predose is an unscheduled visit, then as per the baseline definition, this will be considered as baseline. And unscheduled visits will be taken into consideration for calculating worst-case post baseline value in ECG displays as well. All unscheduled visits will be included in listings. 	
Descriptive Summary Statistics	
Continuous Data	Refer to IDSL Statistical Principle 6.06.1
Categorical Data	N, n, frequency, %
Graphical Displays	

 Refer to IDSL Statistical Principles 7.01 to 7.13. 	

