10.6. Appendix 6: Liver Safety: Required Actions and Follow-up Assessments

Phase I liver chemistry stopping criteria and required follow up assessments

Liver Chemistry Stopping Criteria	
ALT-absolute	
ALT\geq3xULN
 
If ALT\geq3xULN AND bilirubin^{1,2} \geq 2xULN (>35% direct bilirubin) or INR >1.5, Report as an SAE.
 
See additional Actions and Follow Up Assessments listed below

Required Actions and Follow up Assessments	
Actions	Follow Up Assessments

 • Immediately discontinue study intervention • Report the event to GSK within 24 hours • Complete the liver event CRF, and complete an SAE data collection tool if the event also meets the criteria for an SAE² • Perform liver event follow up assessments • Monitor the subject until liver chemistries resolve, stabilise, or return to within Baseline (see MONITORING below) 
MONITORING:
 
If ALT\geq3xULN AND bilirubin \geq 2xULN or INR >1.5
 
 • Repeat liver chemistries (include ALT, aspartate transaminase [AST], alkaline phosphatase, bilirubin and INR) and perform liver event follow up assessments within 24 hrs • Monitor subjects twice weekly until liver chemistries resolve, stabilise or return to within Baseline • A specialist or hepatology consultation is recommended 
If ALT\geq3xULN AND bilirubin < 2xULN and INR \leq1.5:
 
 • Repeat liver chemistries (include ALT, AST, 	
 • Viral hepatitis serology³ • Obtain international normalized ratio (INR) and recheck with each liver chemistry assessment until the transaminases values show downward trend • Obtain blood sample for pharmacokinetic (PK) analysis, obtained within 7 days of last dose⁴ • Serum creatine phosphokinase (CPK) and lactate dehydrogenase (LDH). • Fractionate bilirubin, if total bilirubin\geq2xULN • Obtain complete blood count with differential to assess eosinophilia • Record the appearance or worsening of clinical symptoms of liver injury, or hypersensitivity, on the AE report form • Record use of concomitant medications on the concomitant medications report form including acetaminophen, herbal remedies, other over the counter medications. • Record alcohol use on the liver event alcohol intake case report form 
If ALT\geq3xULN AND bilirubin \geq 2xULN or INR >1.5:
 
 • Anti-nuclear antibody, anti-smooth muscle

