13.7. Appendix 7: Reporting Standards for Missing Data

13.7.1. Premature Withdrawals

Element	Reporting Detail
General	
 • Subject study completion (i.e. as specified in the protocol) was defined as 'A participant is considered to have completed the study if he/she has completed all phases of the study including or the last scheduled procedure shown in the SoA.' • Withdrawn subjects may be replaced in the study. • All available data from participants who were withdrawn from the study will be listed and all available planned data will be included in summary tables and figures, unless otherwise specified.

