3.26.	Safety	LIVER14	Scatter Plot of Maximum vs. Baseline for ALT – Part A	Recommended for larger studies, but not required for smaller studies.	SAC
3.27.	Safety	LIVER14	Scatter Plot of Maximum vs. Baseline for ALT – Part B	Recommended for larger studies, but not required for smaller studies.	SAC

Safety: Figures					
No.	Population	IDSL / Example Shell	Title	Programming Notes	Deliverable [Priority]
3.28.	Safety	LIVER14	Scatter Plot of Maximum vs. Baseline for ALT – Part C	Recommended for larger studies, but not required for smaller studies.	SAC

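### SAP 13.5.2 makes a worst-case exception for ECG but not for laboratory values, so the maximum-ALT plots can omit a participant's true post-baseline maximum

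*SAP*

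**What the plan says.** SAP 13.5.2, under Unscheduled Visits, sets a general rule: "Unscheduled visits will not be included in summary tables and/or figures". Two exceptions follow. One concerns baseline: "for baseline consideration if the latest predose is an unscheduled visit, then as per the baseline definition, this will be considered as baseline". The other concerns a single type of display: "unscheduled visits will be taken into consideration for calculating worst-case post baseline value in ECG displays as well". The section ends with "All unscheduled visits will be included in listings".

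For participants withdrawn from the study, SAP 13.7.1 lists everything but says of summaries that "all available planned data will be included in summary tables and figures", subject to anything specified elsewhere.

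Protocol Appendix 6 (10.6) sets the follow-up once ALT reaches 3xULN. If bilirubin is at least 2xULN or INR exceeds 1.5, liver chemistries are repeated within 24 hours, and then: "Monitor subjects twice weekly until liver chemistries resolve, stabilise or return to within Baseline". If neither holds, the repeat is due at 24 to 72 hours and monitoring is weekly.

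SAP Appendix 12 plans Figures 3.26-3.28, titled "Scatter Plot of Maximum vs. Baseline for ALT", and Tables 3.44-3.46 on hepatobiliary laboratory abnormalities, for Parts A, B and C. No programming note on any of them admits unscheduled values.

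**The concern.** A worst-case display should draw on every post-baseline measurement. The SAP accepts this for ECG and says so, but makes no matching provision for laboratory values. The Appendix 6 repeats are triggered by the event, not by the Schedule of Activities, so a repeat off the scheduled days is unscheduled and stays out of the figures and tables. The treatment is also uneven: an unscheduled ALT can set a participant's baseline but cannot be that participant's post-baseline maximum.

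The liver matters here. Dog liver findings set the exposure limits in Protocol 6.6 and 7.1.6.2, and clinical laboratory values are a primary endpoint. What is at stake is whether a plot labelled as a maximum shows the maximum for the few participants who meet the stopping rule.

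**Working it through.** The plan gives no figure to reproduce. The check sets the repeat-test timing of Protocol Appendix 6 against the scheduled laboratory days.

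**Inputs.** Scheduled safety laboratory days in Part B after the Day 1 dose series (Protocol 1.3; SAP Appendix 2): 14-day schedule, Days 7, 11, 17, 20 and follow-up; 7-day schedule, Days 7, 10, 13 and follow-up. Follow-up is about 14 days after the last dose. If all doses are taken, that is 17 + 14 = Day 31 or 10 + 14 = Day 24.

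**Rule.** For a trigger on scheduled Day d, the repeat is due by Day d+1 (more severe event) or on Days d+1 to d+3 (otherwise).

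| Schedule | Trigger | Within 24 h | 24-72 h | Scheduled lab in that span |
|---|---|---|---|---|
| 14-day | Day 7 | by Day 8 | Days 8-10 | none |
| 14-day | Day 11 | by Day 12 | Days 12-14 | none |
| 14-day | Day 17 | by Day 18 | Days 18-20 | Day 20, at the 72 h limit only |
| 14-day | Day 20 | by Day 21 | Days 21-23 | none |
| 7-day | Day 7 | by Day 8 | Days 8-10 | Day 10, at the 72 h limit only |
| 7-day | Day 10 | by Day 11 | Days 11-13 | Day 13, at the 72 h limit only |
| 7-day | Day 13 | by Day 14 | Days 14-16 | none |

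The 24-hour repeat meets no further scheduled laboratory day in any of the 7 cases. The 24-72 hour repeat can meet one in 3 of 7, and only at its outer limit. Stopping dosing early brings the follow-up visit forward, but not into these spans: a last dose on Day 7 puts it at about Day 21.

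**Parts A and C.** Samples are scheduled at 8, 24, 48 and 72 h after dosing. A trigger at 8 h is followed by a scheduled sample 16 h later (24 - 8), and a trigger at 24 or 48 h by one 24 h later. Overlap is therefore likely until 72 h. The schedules for all parts also carry an early-discontinuation sample.

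**Does anything else bring the off-schedule values back?**
- SAP Appendix 3 uses nominal time outside PK and defines no visit windows.
- SAP 13.6.1 resolves two values in one window by closeness to the target day, so it would not select the higher one.
- The sponsor's display standards apply unless the SAP states otherwise, and 13.5.2 does.

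**Consequence.** Plotted maximum = highest scheduled post-baseline value. True maximum = highest of scheduled and unscheduled values. The first can never exceed the second and falls below it whenever the peak is on an unscheduled repeat. Any error is therefore towards understatement.

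**The case against.** The strongest reply is that little is hidden.

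- **Event summaries.** Tables 3.41-3.43 summarise liver monitoring and stopping events. ALT of at least 3xULN with bilirubin of at least 2xULN (more than 35% direct), or with INR above 1.5, must be reported as an SAE and so reaches Tables 3.14-3.16.
- **Listings.** The flag for potential clinical importance is ALT of at least 2xULN (SAP 13.8.1), so every stopped participant qualifies for Listings 71-73, which show all of that participant's chemistry data. Listings 59-61 cover liver events.
- **Study size.** Safety review rests partly on individual data. The notes say that a listing may replace Tables 3.44-3.46 when events are few, and that Figures 3.26-3.28 are optional in small studies.

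All of this stands, and it limits the consequence. It does not remove the point: the displays are on the list for final reporting, SAP 13.5.2 keeps subject-level listings out of the main body of the study report, and a count of stopping events need not show how high ALT went.

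A reader might draw four stronger conclusions that the documents do not support.

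- **Every Appendix 6 repeat is excluded.** Some coincide with scheduled or early-discontinuation samples, as shown above.
- **SAP 13.7.1 shuts out all stopped participants a second time.** It covers withdrawal from the study, whereas Protocol 7.1 keeps a participant who stops study intervention in the study. Withdrawal follows under Protocol 7.1.3 if the event is an SAE. The sentence also does not say that planned data alone may be used, and it allows exceptions.
- **Tables 3.44-3.46 would miss combined ALT and bilirubin rises.** The shell (LIVER10) is not in the documents, so its categories are unknown.
- **The understatement is large.** Suppose ALT of 3.2xULN on Day 7 and 8xULN on a Day 9 repeat. To be plotted at 3.2xULN, ALT would have to fall 8/3.2 = 2.5-fold by the next scheduled sample, 24 h later (7-day) or 48 h later (14-day). The documents give no support for such a fall. A slower one would put a higher scheduled value into the plot.

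**Conclusion.** The point holds with limited reach. Read as written, SAP 13.5.2 lets Figures 3.26-3.28, and Tables 3.44-3.46 to the extent that they contain worst-case categories, omit a participant's true post-baseline maximum. Part B is most exposed.

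Three assumptions carry this: a liver event occurs, its peak falls on an unscheduled sample, and the programmers apply 13.5.2 in preference to any default in the LIVER10 and LIVER14 shells, which are not supplied. If those shells admit unscheduled values, the SAP contradicts them and still needs correcting.

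No expected size can be given. With 9 active participants per Part B cohort, one affected participant is 1/9 = 11% of the dose group; that is a share, not a likelihood. A participant whose triggering ALT came from a scheduled sample still contributes a value of at least 3xULN. What can be lost from these displays is a higher later peak, or a rise in another liver test seen only on repeat. A reader might infer that liver safety data are lost or that liver events would go unreported; neither follows, because the values are listed and the events are summarised elsewhere.

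**What to change.** In SAP 13.5.2, extend the ECG worst-case exception to every maximum or worst-case post-baseline laboratory display, naming Figures 3.26-3.28 and Tables 3.44-3.46. State that by-visit summaries stay on scheduled visits only, so that event-driven extra samples do not distort visit means.

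In SAP 13.7.1, add a cross-reference to that exception, so that the reference to planned data does not exclude these values for participants withdrawn from the study.

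The cost is about two sentences and one programming flag. No new data are collected and trial conduct does not change. The edit should be made before database freeze.
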